## **SAMPLE SIZE**

40 women will be recruited into the study in order to achieve at least 30 evaluable subjects (15 in each treatment arm) over the 12 months duration of the study. Based on the standard deviation for fasting glucose concentrations reported from the NHANES II study, measurable data from 30 subjects (15 in each group) will have 80% power to find an inter-group difference as small as 8 mg/dL at a p-value of 0.05 (13).

## **PRIMARY EFFICACY MEASURES**

The primary measure used to substantiate the primary study objective will be maternal glucose control as reflected by fasting values from glucose monitor data.

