**PRIMARY OBJECTIVE**

Compare the efficacy and safety of three daily injections of Humalog® Mix50/50™ to six daily injections of Humalog® and Humulin N® insulin, by fasting glucose measurements.

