## **METHODS**

Subjects will be randomized 1:1 to receive usual insulin treatment of six injections daily (Humalog® injected three times daily before meals plus Humulin N® insulin injected at 8am, 4pm and midnight) as diagrammed in Figure 1, or 3 injections of Humalog® Mix50/50™ (injected only before meals) as diagrammed in Figure 2.

Baseline measures will include glucose tolerance test data, height, weight, and A1C by DCA2000+. In addition to the standard instruction to test blood glucose pre- and one-hour postprandial, all participants will be asked to test blood glucose levels at 3 a.m. Patients on the Humalog® Mix50/50™ arm of the study will be initially prescribed insulin doses of 0.3 times their weight in kilograms to be taken before each of three meals. Those on the standard therapy arm will be initially prescribed insulin doses calculated at 0.15 times their weight in kilograms for each of their 6 injections.

---

 We shall use American Diabetes Association criteria for diagnosis of GDM: blood glucose concentration >140 mg/dL one hour after administration of a 50 gram glucose load, followed by an oral glucose tolerance test (OGTT) in which 2 or more of the readings are at or above 95 mg/dL fasting, 180 mg/dL at one hour, 155 mg/dL at 2 hours and 145 mg/dL 3 hours after administration of a 100 gram glucose load (12).

Participants will be seen weekly for adjustment in dosages based on their food records, downloaded glucose monitor data and A1 C levels. Subjects in the study group whose fasting glucose exceeds 90 mg/dl will be prescribed Humalog® Mix75/25™ at their evening meal rather than Humalog® Mix50/50™. Subjects will be discontinued from the study if their 3 a.m. blood glucose concentration falls below 55 mg/dL that is unresponsive to a snack at bedtime or if their fasting blood glucose is greater than 90mg/dL despite increasing doses of Humalog® Mix50/50™ at the evening meal followed by treating with Humalog® Mix75/25™ at the evening meal.

Maternal weight will be recorded at each visit. Participants will be asked to bring their supply of insulin pens to every other visit, for which they will be paid ten dollars to maximize cooperation with this essential aspect of the research. The insulin pens will be counted as measures of adherence.

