## **STATISTICAL ANALYSIS**

Data analysis will be done using SAS for Windows version 9. Differences between groups in continuous variables (glucose, A1C, birth weight etc.) will be compared with t-tests and potential confounders (age, race/ethnicity etc.) will be controlled for with linear regression. Differences in categorical variables (hypoglycemic events, macrosomia, type of delivery

etc.) will be evaluated using chi-square or Fisher's tests as appropriate. Our tests will be testing the hypothesis that the two treatments are different and the null hypothesis will be equivalence.

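### The primary t-test is set on repeated fasting meter values without one value per woman and without the baseline fasting glucose as a covariate

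*Protocol*

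**What the plan says.** The Primary Objective compares the two regimens "by fasting glucose measurements", with no time point. Primary Efficacy Measures describes the endpoint as the mother's glucose control, judged by "fasting values from glucose monitor data". Neither section says whether a woman's readings are averaged, which days count, or whether a single reading is taken. A1C, a secondary measure, is by contrast tied to baseline and the end of the protocol.

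The readings are repeated. Under Methods, "Participants will be seen weekly for adjustment in dosages based on their food records, downloaded glucose monitor data" and A1C, so meter data accumulate for as long as a woman is treated.

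Under Statistical Analysis, "Differences between groups in continuous variables (glucose, A1C, birth weight etc.) will be compared with t-tests". Linear regression is then offered to control for confounders, with age and race/ethnicity as the named examples. Neither method has a term for several readings from one woman. Baseline fasting glucose is not named, although Study Design has women log fingerstick values before and after meals, and selects them for the trial on those values after a week of diet and exercise.

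Sample Size counts women: 15 evaluable per arm, 80% power for 8 mg/dL at 0.05.

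**The concern.** A two-sample t-test assumes independent observations. Fasting readings from one woman are correlated, so the stated test fits the stated measure only after a reduction step that the protocol does not describe. If someone ran the test on the readings as they come off the meter, the standard error would be too small and false differences would be common. If the reduction is made but left unstated, several summaries remain open once the data are in hand.

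The second part concerns efficiency. With 15 women per arm, the strongest available predictor of on-treatment fasting glucose is likely to be fasting glucose just before treatment. The protocol has women record it, then names only age and race/ethnicity for adjustment. In a trial this small, that may give up useful precision.

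**Working it through.** **Inputs.** From Sample Size: n = 15 per arm, difference 8 mg/dL, power 80%, significance level 0.05 (taken as two-sided). The SD is attributed to NHANES II but not printed. Readings per woman (m), intra-woman correlation (ICC) and the correlation r between baseline and outcome are not in the protocol and are assumed.

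**1. The protocol's own figure.** Solving the power statement for the SD:
- Normal approximation: 8 / [(1.960 + 0.842) × √(2/15)] = 8 / (2.802 × 0.3651) = 7.82 mg/dL.
- Exact noncentral t, 28 df: 7.55 mg/dL.

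The 80% can be neither confirmed nor refuted without the SD. I use 7.55 below. The standard error of the difference is then 7.55 × 0.3651 = 2.76 mg/dL, and the 95% CI half-width is 2.048 × 2.756 = 5.65 mg/dL.

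**2. Type I error if readings were pooled.** The variance of the arm difference is understated by about D = 1 + (m − 1) × ICC, so the true error rate is about 2Φ(−1.96/√D).

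| m | ICC | D | 1.96/√D | Type I error |
|---|---|---|---|---|
| 7 | 0.1 | 1.6 | 1.55 | 12% |
| 7 | 0.3 | 2.8 | 1.17 | 24% |
| 28 | 0.3 | 9.1 | 0.65 | 52% |
| 60 | 0.3 | 18.7 | 0.45 | 65% |

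Simulation of the pooled t-test, with 15 women per arm and 20,000 or more trials per setting, gives the same figures. With one mean per woman, the simulated error is 4.6–4.9% across m from 7 to 70 and ICC from 0.1 to 0.7.

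**3. Gain from adjusting for baseline.** With one value per woman, regression on arm and baseline leaves a residual SD of 7.55 × √(1 − r²) on 30 − 3 = 27 df.

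| r | Residual SD | SE | 8/SE | Power | 95% CI half-width |
|---|---|---|---|---|---|
| t-test, no covariate | 7.55 | 2.76 | 2.90 | 80% | 5.65 |
| 0 | 7.55 | 2.76 | 2.90 | 79.9% | 5.66 |
| 0.3 | 7.20 | 2.63 | 3.04 | 83.5% | 5.40 |
| 0.5 | 6.54 | 2.39 | 3.35 | 90% | 4.90 |
| 0.6 | 6.04 | 2.21 | 3.63 | 94% | 4.52 |

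Allowing also for chance imbalance in baseline (variance × about 1 + 1/26), power is about 82% at r = 0.3 and 93% at r = 0.6. On that stricter count the break-even is near r = 0.2 (80%), and an uninformative covariate would cost about two points (78%).

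**The case against.** The strongest reply is that the protocol never treats readings as independent. The only section that fixes a unit, Sample Size, counts 15 women per group, and a t-test of that size points to one value each. This stands. The error rates in step 2 describe what would happen under pooling, not what the trial plans.

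A second reply is that data reduction and analysis windows are often left to a SAP, which may exist. For the choice of window this is fair, and an unstated window alone would not be a finding. It is weaker for the method, because the protocol itself prescribes the t-test. The list of confounders is open-ended and could be stretched to include baseline glucose, but it does not name it.

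Two stronger readings are tempting and not supported:

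- **That the test must either inflate type I error or dilute a real difference.** A per-woman mean over a late period also fits the text and has neither fault.
- **That early weeks of dose adjustment dilute the contrast toward the hoped-for equivalence**, given that "the null hypothesis will be equivalence". The arithmetic works: if 20% or 40% of averaged readings carried no difference, 8 mg/dL would become 6.4 or 4.8 and power 61% or 39%. The premise does not. Starting doses give equal daily totals (3 × 0.3 = 6 × 0.15 = 0.9 times weight), but equal totals do not imply equal fasting values. One arm has a midnight injection and the other injects only at meals, so the overnight regimens differ from the first day. Methods also links fasting values above 90 mg/dL to an evening insulin change and later to discontinuation in the Mix50/50 arm, which could bring late values together and leave the larger contrast early. Weekly adjustment has no stated end, so no period after titration can be identified. How a non-significant result is to be read is a separate matter of the hypothesis set-up.

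**Conclusion.** The concern holds in a limited form. The protocol applies a plain t-test to a repeatedly measured primary variable without stating one value per woman, and it does not name the baseline fasting glucose that women already record. Type I error would be about 12% to 65% over the m = 7, ICC 0.1 to m = 60, ICC 0.3 settings, but only if readings were pooled, which the sample-size statement suggests is not intended. Averaging within each woman restores about 5%.

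Baseline adjustment would take power for 8 mg/dL from 80% to about 84–94% (82–93% allowing for chance imbalance). This rests on the implied SD of 7.55 applying to the per-woman mean and on r between 0.3 and 0.6. Because women are selected on diet-week glucose, the baseline range may be narrowed and r may lie toward the lower end. No conclusion follows about the direction in which early or late readings would move the result. This should be changed, but it does not invalidate the design.

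**What to change.** In Primary Efficacy Measures, define the primary value as each woman's mean fasting meter glucose over a prespecified period, using all her readings in that period whatever formulation she is on. Name one period (whole treatment or a late window) as primary and the other as a sensitivity analysis, in an order fixed before the data are seen.

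In Statistical Analysis, replace the t-test for this endpoint by linear regression of that one value on arm plus the woman's mean fasting glucose from the diet-only week, and report the adjusted difference with its 95% CI.

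Add the diet-week fasting mean to the baseline measures in Methods, which now list glucose tolerance test data, height, weight and A1C but not these readings. Where a woman's diet-week log cannot be retrieved, the fasting value from her glucose tolerance test is a possible prespecified substitute.

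The cost is a few sentences, one degree of freedom and the work of retrieving the diet-week readings. No extra visit or measurement is needed. Means over a shorter window are noisier, which is a reason to report both periods.

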## **SECONDARY EFFICACY MEASURES**

The maternal A1C will be measured by Bayer DCA2000+ at baseline and at end of protocol. The 3 a.m. glucose records will be assessed for nocturnal hypoglycemia. Maternal weight gain will be assessed as an indicator of over-insulinization. In addition, we will analyze baby birth weight percentile, APGAR scores, cord blood insulin levels and mode of delivery as measures of fetal outcome. We will use insulin pen count data as an indicator of maternal adherence to the therapy regimen.

## **STATISTICAL ANALYSIS**

Data analysis will be done using SAS for Windows version 9. Differences between groups in continuous variables (glucose, A1C, birth weight etc.) will be compared with t-tests and potential confounders (age, race/ethnicity etc.) will be controlled for with linear regression. Differences in categorical variables (hypoglycemic events, macrosomia, type of delivery

etc.) will be evaluated using chi-square or Fisher's tests as appropriate. Our tests will be testing the hypothesis that the two treatments are different and the null hypothesis will be equivalence.

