## **STUDY DESIGN**

Women diagnosed with gestational diabetes receive diet and exercise education. They are instructed to record their pre- and post-prandial glucose measurements obtained by fingerstick. Following one week of diet and exercise therapy, patients with fasting glucose levels >90 mg/dL or postprandial glucose level >120 mg/dL will be recruited to this study.

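### A1C and fasting glucose are compared between arms by t-test, and the baseline value already collected is not named as a covariate: a possible loss of precision, clearest for A1C

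*Protocol*

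**What the plan says.** The protocol's Statistical Analysis section groups glucose, A1C and birth weight as continuous variables whose between-group differences "will be compared with t-tests and potential confounders (age, race/ethnicity etc.) will be controlled for with linear regression". No section names the baseline value of an outcome as a covariate.

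The candidate covariates are in hand:

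- Methods: "Baseline measures will include glucose tolerance test data, height, weight, and A1C by DCA2000". The diagnostic criteria in the footnote ("2 or more of the readings are at or above 95 mg/dL fasting") show that the tolerance test includes a fasting reading.
- Secondary Efficacy Measures: A1C is measured on the same type of device at entry and again at the end.
- Secondary Objectives, item 5: baseline A1C is used for the within-group comparison, while the between-group comparison is of end values only.
- Study Design: during the diet week, before recruitment, "They are instructed to record their pre- and post-prandial glucose measurements obtained by fingerstick". These readings are not listed among the baseline measures.

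The primary measure is "maternal glucose control as reflected by fasting values from glucose monitor data". The Sample Size section says that 15 evaluable women per arm "will have 80% power to find an inter-group difference as small as 8 mg/dL at a p-value of 0.05".

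**The concern.** When an outcome has a measured baseline value, a linear model on arm plus that value usually estimates the treatment difference more precisely than a t-test on the final values, as long as baseline predicts outcome well enough to repay one degree of freedom and a small penalty for chance imbalance. With 15 women per arm there is little precision to spare. The Study Hypothesis and Anticipated Findings sections expect equivalence or non-inferiority, so the width of the interval largely decides what the trial can show.

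The protocol names its test and gives examples of covariates, and the examples leave out the variable most directly tied to the outcome. Under randomisation a baseline value is a prognostic covariate rather than a confounder, so the heading of potential confounders does not lead an analyst to it.

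**Working it through.** **Inputs.** From Sample Size: 15 evaluable women per arm, difference 8 mg/dL, power 80%, p-value 0.05. From Methods: 1:1 allocation. Assumed: a two-sided test (sidedness is not stated) and the correlation r between baseline and outcome (not in the protocol), taken from 0 to 0.5.

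**Step 1. The plan's own figure.** No standard deviation is printed, so the 80% cannot be checked independently; it can only be solved backwards. With the noncentral t on 28 df, 80% power at 8 mg/dL requires SD = 7.55 mg/dL. Then:

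- SE = 7.549 × √(2/15) = 2.756
- 95% half-width = 2.048 × 2.756 = 5.65 mg/dL

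**Step 2. Baseline-adjusted model.** One covariate leaves 27 df (critical value 2.052). The variance of the treatment difference is multiplied by

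(1 − r²) × (1 + 1/26),

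where the second term is the expected cost of chance imbalance with N = 30. The equivalent unadjusted sample size is 15 divided by this factor.

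| r (assumed) | Variance factor | Power at 8 mg/dL | Half-width, mg/dL | Change in width | Equivalent n per arm |
|---|---|---|---|---|---|
| t-test | 1 | 80.0% | 5.65 | – | 15 |
| 0 | 1.038 | 78.4% | 5.76 | +2.1% | 14.4 |
| 0.1 | 1.028 | 78.8% | 5.73 | +1.6% | 14.6 |
| 0.2 | 0.997 | 80.0% | 5.65 | 0.0% | 15.0 |
| 0.3 | 0.945 | 82.1% | 5.50 | −2.6% | 15.9 |
| 0.5 | 0.779 | 88.7% | 4.99 | −11.6% | 19.3 |

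Example, r = 0.3: 0.91 × 1.0385 = 0.945; SE = 2.756 × √0.945 = 2.679; half-width = 2.052 × 2.679 = 5.50.

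**Step 3. Break-even.** The widths are equal when (1 − r²) × (27/26) × (2.052/2.048)² = 1, which gives r = 0.20.

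**Step 4. Simulation check** (40,000 trials per setting, true difference 8). Power of the t-test and the adjusted model was 0.798 and 0.784 at r = 0, 0.798 and 0.798 at r = 0.2, 0.803 and 0.822 at r = 0.3, and 0.800 and 0.886 at r = 0.5. The type I error of the adjusted model was 0.048 to 0.051.

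**Step 5. What carries over to A1C.** The change in width needs no SD, so that column applies to A1C with 15 women per arm. The power and mg/dL columns apply only to fasting glucose, and only with the back-solved SD.

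**Step 6. How large r may be.**

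- *A1C*: same measure and same type of device at both times, so the baseline is like for like.
- *Fasting glucose*: the tolerance-test value is one diagnostic reading taken before the diet week, whereas the endpoint comes from home monitor data. If the reliability of that reading is 0.5 to 0.8 (assumed), observed r = true r × √reliability, and the true r needed to break even rises to 0.28 to 0.22.
- Other features may lower r further: the entry rule ("patients with fasting glucose levels >90 mg/dL or postprandial glucose level >120 mg/dL will be recruited to this study"), weekly titration ("Participants will be seen weekly for adjustment in dosages based on their food records, downloaded glucose monitor data and A1 C levels"), and the Methods rule that discontinues women whose fasting value stays above 90 mg/dL despite the evening-dose changes, which can cut off the upper end of the outcome among evaluable women.

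**The case against.** The strongest reply is that nothing here is stated wrongly. The t-test is valid, the covariate list ends in an open-ended term, and an analysis plan that is not shown could add the baseline value. On this view it is a choice between two valid analyses, and the gain rests on a correlation found nowhere in the protocol. At r = 0 or 0.1 the adjusted analysis is slightly worse than the planned one. For the primary endpoint there is no like-for-like monitor baseline on the list, and the protocol's own features point towards a low r.

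Much of this stands. The baseline value is unnamed, not excluded. For fasting glucose the gain may be nil, and the 88.7% power at r = 0.5 should not be expected from a single tolerance-test reading.

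It does not remove the point. The section fixes the t-test as the between-group comparison, and an open-ended list of confounders does not supply a prognostic covariate. The cost of being wrong is capped and is smaller than what the planned regression already risks. With q covariates that predict nothing, the variance factor is 1 + q/(27 − q). Two coefficients give a 4.3% wider interval and 76.7% power; four (for example age plus three race/ethnicity indicators, an assumed coding) give 9.2% and 72.9%.

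A reader might also infer that the t-test biases the comparison, or that the primary analysis forfeits substantial power. Neither is supported: allocation is randomised, and no figure in the protocol places r well above break-even for fasting glucose.

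**Conclusion.** The point holds as a possible loss of precision from a valid analysis. It is firmest for A1C, where an identical baseline measure is collected and already used within groups but is not named for the comparison between groups. For fasting glucose it is a modest improvement with an uncertain return.

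The range runs from a 2.1% wider interval (r = 0), through no change (r about 0.2), to 2.6% narrower (r = 0.3) and 11.6% narrower (r = 0.5). In power at 8 mg/dL that is 78.4% to 88.7% against 80.0%. These figures assume 15 evaluable women per arm, a linear relation between baseline and outcome, and the stated values of r; the power figures also assume a two-sided test and an SD of 7.55 mg/dL.

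**What to change.** In Statistical Analysis, state that:

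1. End-of-protocol A1C is compared between groups with a linear model on arm plus baseline A1C. The within-group comparison in the Secondary Objectives can stay as description.
2. On-treatment fasting glucose is compared with a linear model on arm plus one covariate named in advance, the fasting tolerance-test value.
3. The unadjusted t-tests are kept as sensitivity analyses.

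Both covariates are already listed baseline measures, so the change is one of wording, with no new data and no more women. The diet-week fingerstick mean may be closer in kind to the endpoint, but it is not listed as study data and would have to be captured, so the fix does not rely on it. The statistical cost is one degree of freedom per model and, if baseline proves uninformative, the 2.1% wider interval shown above.

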**PROTOCOL**  
**HUMALOG® MIX50/50™ FOR THE TREATMENT OF INSULIN REQUIRING**  
**GESTATIONAL DIABETES**

**RATIONALE**

Controlling hyperglycemia during pregnancy decreases the risk of adverse neonatal and maternal outcomes. Not only must fasting glucose be normalized, but clinical evidence also indicates that controlling postprandial hyperglycemia will significantly reduce the risk of adverse neonatal and maternal outcomes (1-2).

Standard therapy to achieve near-normal glycemia in gestational diabetes involves combining intermediate-acting basal (NPH) insulin with rapid-acting insulin (insulin lispro), thereby requiring 6 daily injections (Figure 1). Premixed Humalog® Mix50/50™ has the potential advantage over combination rapid-acting plus NPH insulin because it involves fewer injections, and those injections are associated with mealtime (Figure 2). The potential downside to the premixed formulation is nocturnal hypoglycemia associated with the time lag between the dinner and breakfast dose. This study will evaluate the efficacy and safety of Humalog® Mix50/50™ compared to that of Humalog® plus Humulin N® insulin for the treatment of insulin-requiring patients with gestational diabetes mellitus, while monitoring glucose control, intrauterine growth and assessing pregnancy outcomes.

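### Hypoglycemic events are assigned to a chi-square or Fisher's test; read as one yes/no per woman, this discards repeat events and time at risk for the trial's named safety concern

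*Protocol*

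**What the plan says.** The Rationale names the safety question: "The potential downside to the premixed formulation is nocturnal hypoglycemia associated with the time lag between the dinner and breakfast dose". Secondary objective 1 is to compare the incidence of maternal hypoglycemic events, and Anticipated Findings says that the risk, above all at night, needs careful assessment.

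The data are repeated measurements. Under Methods, "all participants will be asked to test blood glucose levels at 3 a.m", and weekly dose adjustment draws on "downloaded glucose monitor data and A1 C levels". Under Secondary Efficacy Measures, "The 3 a.m. glucose records will be assessed for nocturnal hypoglycemia", with no method given.

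The only method stated for events is in Statistical Analysis. The list that opens "Differences in categorical variables (hypoglycemic events, macrosomia, type of delivery" ends with the statement that these variables "will be evaluated using chi-square or Fisher's tests as appropriate". The protocol defines neither a hypoglycemic event nor the unit of analysis (woman or event), and names no count, rate or time-at-risk method for events.

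Time at risk varies. Entry is possible at any gestation from 13 weeks. Methods has two discontinuation rules. One follows a low at night that a bedtime snack does not correct: "Subjects will be discontinued from the study if their 3 a.m. blood glucose concentration falls below 55 mg/dL". The other applies "if their fasting blood glucose is greater than 90mg/dL despite increasing doses of" Mix50/50 and then a change to Mix75/25, so it is worded only for the Mix products.

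**The concern.** Grouping hypoglycemia with macrosomia and type of delivery most naturally means one yes/no per woman. That summary cannot tell one low from twenty, and it takes no account of whether a woman was observed for four weeks or twenty. The objective speaks of incidence of events, which is closer to a rate than to a share of women affected.

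The other reading, a chi-square on events pooled as independent units, is worse. Events within one woman are correlated, so the test would reject too often.

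At stake is the comparison that the protocol itself singles out as the possible price of fewer injections. The t-test on glucose does not fill the gap, because it compares means and not lows.

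**Working it through.** **The plan's own figure.** Sample Size claims 80% power for 8 mg/dL in fasting glucose with 15 women per arm. No SD is printed, so the claim can be neither confirmed nor refuted; it implies SD = 8 × √(15/2) / (1.96 + 0.84) ≈ 7.8 mg/dL (normal, two-sided). No figure is given for hypoglycemia, so everything below rests on assumed inputs.

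**Inputs.** From the protocol: 15 evaluable women per arm and a 0.05 level (taken as two-sided). Assumed: follow-up uniform over 4-20 weeks; event counts Poisson given a woman-specific rate, with gamma variation between women (shape 1); control rate r from 0.02 to 0.5 events per week; Mix rate 2r.

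**Step 1. Share of women with any event.** With shape 1, P(any event by week T) = 1 − 1/(1 + rT). Averaged over T from a to b weeks:

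P = 1 − ln[(1 + br)/(1 + ar)] / [(b − a)r]

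At r = 0.1 and 4-20 weeks: 1 − ln(3/1.4)/1.6 = 52%. At r = 0.2: 1 − ln(5/1.8)/3.2 = 68%. At r = 0.5 and 1.0 the shares are 84% and 91%. A doubled rate therefore moves the yes/no share by 16 points at 0.1 per week but by only 7 points at 0.5, because most women in both arms are already a yes.

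**Step 2. Power for a doubled rate, by simulation.** Planned test: chi-square if all expected counts are at least 5, otherwise Fisher.

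| Control rate per week | 0.02 | 0.05 | 0.1 | 0.3 | 0.5 |
|---|---|---|---|---|---|
| Planned test | 7% | 13% | 12% | 5% | 2% |
| Uncorrected chi-square throughout | 13% | 14% | 14% | 10% | 7% |
| t-test on woman-level rates | 10% | 18% | 23% | 30% | 31% |
| Permutation of arms by woman, on rates | 13% | 20% | 26% | 34% | 34% |

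For a tripled rate the planned test has 18/27/22/8/3% and the permutation test 30/47/59/69/70%. With equal follow-up, type I error is 1.4-4.3% for the planned test and 4.4-5.2% for the permutation test.

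**Step 3. Unequal follow-up (illustrative).** Take r = 0.1 and halve follow-up (2-10 weeks) in half of the Mix women.

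- Equal true rates: a halved woman has P = 1 − ln(2/1.2)/0.8 = 36%, so the Mix share is (52 + 36)/2 = 44% against 52% in control. Mix looks safer although the rates are equal.
- Mix rate doubled: (68 + 52)/2 = 60% against 52%. A doubling shows as 8 points instead of 16.
- The median rate ratio is 1.00 and 2.0 in the two cases.
- If all Mix follow-up is halved and true rates are equal, the shares are 36% v 52% and the planned test rejects in 12.8% of trials.

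**Step 4. Events pooled as independent units.** With equal rates and equal follow-up (0.05-0.3 per week, gamma variance 0.5-1), type I error was 7-36%.

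**Step 5. Limits of the rate analysis.** If 10/25/50% of events end a woman's participation, the median rate ratio is 1.92/1.83/1.77 for a true 2.0 (0.1 per week). With 12 v 18 women and all Mix follow-up halved, the permutation test has about 7% type I error.

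**The case against.** **The sentence is generic and the SAP is not shown.** The unit, counting rule and denominator are often left to a SAP. That stands: the protocol does not fix one yes/no per woman, and it would be wrong to say so. What it does fix is a categorical test for events that recur, and neither reading of that test suits them.

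**The share of women with any event is a common and valid safety summary.** This also stands when follow-up is similar, as the type I error in step 2 shows. A reader might infer that the planned test is invalid or biased towards the Mix arm. The documents do not support that. Variable entry from 13 weeks is balanced in expectation by 1:1 randomization, and women stopped for a 3 a.m. low already count as a yes. Only the fasting rule worded for the Mix products gives a route to shorter follow-up in one arm, and the documents do not show whether it will act or how strongly.

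**The gain depends on invented rates.** Partly true. At 0.02 per week, uncorrected chi-square already matches the permutation test (13% each). The gain is large only when events are common.

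**A permutation test with an inverted interval is more than is needed.** Largely true. A t-test on woman-level rates, a tool the protocol already names, comes within about 4 points of the permutation test.

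**Counting events brings its own difficulties.** True. The event must be defined. Women are only asked to test at 3 a.m., and how often is not stated, so a woman who tests less would appear safer if weeks alone were the denominator.

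**Conclusion.** The point holds as a cheap improvement, not as an error that invalidates the analysis. For its named safety concern, the protocol chooses a test that, on the natural reading, leaves unused the event counts and time at risk that the planned monitoring can supply. For a doubled rate under the stated assumptions, about 2-13% power becomes about 10-34%, and the rate ratio allows for unequal follow-up where the yes/no share does not. The bias from unequal follow-up is conditional; its direction and size are unknown.

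A reader might also blame the test for the trial's weak ability to detect a safety difference. That goes too far: the weakness comes mainly from having 30 women, and no analysis removes it. Confidence is moderate, because every rate, spread and follow-up length is assumed and an unseen SAP may refine the method.

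**What to change.** In Statistical Analysis, take hypoglycemic events out of the categorical list and write instead:

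- **Event.** State before analysis which glucose readings or symptoms count, with at most one event per woman per day (per night for 3 a.m. readings).
- **Comparison.** Compare each woman's events per week on study treatment between arms, by a t-test on the woman-level rates or a permutation of arm labels by woman. Report the rate ratio with a 95% CI.
- **3 a.m. events.** Use the number of 3 a.m. readings taken as the denominator, or report it by arm, so that missed tests do not pass for safety.
- **Context.** Report weeks at risk and discontinuations by arm.
- **Supportive.** Keep the proportion with any event (chi-square or Fisher), and keep those tests for macrosomia and type of delivery.
- **Interpretation.** State that a non-significant result is not evidence of equivalence, and that stopping for a 3 a.m. low pulls the rate ratio toward 1.

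Cost: a counting rule and slightly more analysis. No new visits or tests are needed, since the 3 a.m. tests and meter downloads are already planned. Power stays low and the interval will be wide: if it is obtained by inverting the permutation test, its median limits for a true ratio of 2 are about 0.8 to 4.2 at 0.1 events per week, with 93-94% coverage. The permutation test is only approximate (about 5-7% type I error) if arm sizes and follow-up both differ.
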